## General characteristics of analysis:

- The predictor of interest in all regression models will be the randomization group: 0=control, 1=intervention.
- Regression models will be automatically adjusted for hospital site and ADRD status (as defined at the time of randomization). There will be no other covariates in the models.
- For Cox models, we will use Stata's "exactp" method for correcting for ties unless there are problems with that method, in which case we will use the Efron method. (See page 4.)

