We will conduct this study with a diverse population drawn from 3 hospitals at UW Medicine, including a university hospital (UW Medical Center, UWMC), a county, safety-net hospital (Harborview Medical Center, HMC), and a community hospital (Northwest Hospital and Medical Center, NWHMC). UWMC provides specialist care for the Pacific Northwest region and has 529 acute care beds and 75 ICU beds. HMC is operated by the University of Washington and has 413 acute care beds and 94 ICU beds. HMC is the only Level 1 Trauma Center serving five states, and its mission population includes inner city poor, recent immigrants, and persons with HIV/AIDS. NWHMC is a community hospital with 218 acute care beds and 15 ICU beds, serving north Seattle with a large geriatric and nursing home resident population. Our prior studies have included each of these sites.^{29,30,79} These 3 sites offer the advantage of caring for diverse patients while also using a unified EHR incorporating EPIC systems into a platform we have been able to access and use.¹⁶⁻²¹

c) Patient population

Eligible patients over 55 will be identified by ICD-10 codes for one or more of the nine chronic conditions used by the Dartmouth Atlas:¹³⁴ dementia, malignant cancer/leukemia, chronic pulmonary disease, coronary artery disease, heart failure, chronic liver disease, chronic renal disease, diabetes with end-organ damage, and peripheral vascular disease. These nine conditions account for 90% of deaths among Medicare beneficiaries in the US.^{135,136} To increase inclusivity of important and under-studied populations, we will also include all hospitalized patients over age 80. Among patients meeting these criteria, we will include only those with no identified documentation of goals-of-care discussions during the current hospitalization and prior to enrollment. For Trial 2, eligible patients or their surrogates will have sufficient English language proficiency to complete surveys.

d) Description of participants

We will collect the following information about study participants.

Patients: Age, race, ethnicity, sex, comorbidities and acute severity of illness including the National Early Warning Score (NEWS). For Trial 2, we will additionally collect education, marital status, health status (SF-1) and income.

Families: Age, race, ethnicity, sex, education, marital status, health status (SF-1), relationship to patient, living situation related to patient.

Clinicians: Age, race, ethnicity, sex, education.

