e) Sampling patients with ADRD

Given the dramatically increasing prevalence of ADRD in the US and the rising intensity of care among these patients,^{11,13} it is particularly important that we understand the effect of interventions to improve quality of palliative care in this group. We designed both trials to be powered to examine heterogeneity of treatment effects (HTE) in this important group. For Trial 1, we will plan to continue recruitment to enhance power in this subgroup. For Trial 2, we will prioritize recruitment of patients with ADRD to maximize this subgroup sample size. We hypothesize that the interventions will be equally effective in this population, but that the proportion of patients with decisional capacity will be lower (enrolling more family members). However, we believe it is important to explicitly examine this hypothesis given the unique features of intensity of care at the end of life for this important and increasing population.

f) Randomization

Patients are randomized in a 1:1 ratio in Trial 1 and 1:1:1 ratio in Trial 2 using variable size blocks and stratified for hospital and ADRD vs. no ADRD. Participating family members or legal surrogate decision makers are assigned to the same arm as the corresponding patient.

g) Intervention

Clinician-facing Jumpstart: First, we use automated methods to examine inpatient and outpatient EHR notes prior to the current admission, identifying current code status as well as all prior POLST forms and advance directives; this information is included on Jumpstart Guides to inform discussions. Second, we deliver the Jumpstart Guide to the primary hospital team (all attending and resident physicians and advanced practice providers) via secure email and either a page (Trial 1) or Epic SecureChat message (Trial 2) alerting the physicians to the presence of the Jumpstart Guide in their email, with the addition of in-person delivery of a paper version in Trial 2 only.

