Costs of care	Intensity of care/intervention costs	EHR: During hospital stay, 30 and 90 days post-randomization.
All-cause mortality at 90 days and 1 year	All-cause mortality	Washington State death certificates
Aim 2 outcomes (not used in Aim 1 since the Trial 1 is a pragmatic trial without contact with patients or family members)		
Patient/family-reported discussion of goals ^{9,25}	Goals-of-care discussion occurrence	Survey: 3-5 days & 4-6 weeks post-randomization

Quality of Communication (QOC) ^{24,26,28}	Quality of communication	Survey: 3-5 days post randomization
SUPPORT question ³¹	Goal-concordant care	Survey: 3-5 days & 4-6 weeks post-randomization
HADS – anxiety and depression ^{36,37}	Symptoms of anxiety & depression	Survey: 4-6 weeks post-randomization
EQ-5D-5L	Health-related QOL	Survey: 4-6 weeks post-randomization
Patient/family reported ED, hospitalization and outpatient utilization	Healthcare utilization	Survey: 4-6 weeks post-randomization
CollaboRATE ⁶⁰	Shared decision-making	Survey: 3-5 days post randomization

6) Analyses

We will follow the intention-to-treat principle for all analyses.

a) Primary Outcome (presence of goals of care discussion within 30 days after randomization)

The effect of intervention on the primary outcome will be quantified by the difference in proportions and evaluated with a linear regression model with robust standard errors. The predictor of interest is randomization arm (Clinician-facing Jumpstart or usual care for Trial 1; or Clinician-facing Jumpstart, Bi-directional Jumpstart, or usual care for Trial 2). The model will adjust for hospital site and ADRD status, since randomization is stratified on these factors. This model assumes the effect of intervention is the same for patients with and without ADRD. We will also include an interaction between randomization arm and ADRD, which allows the effect of intervention to vary by ADRD status and allows evaluation of the effect among those with and without ADRD. We will evaluate the timing of goals-of-care discussions with a Cox proportional hazards model.

b) Additional Outcomes

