Trial 1: With a total sample size of 2000 (1000 per group), two-sided significance level (α) of 0.05, and a variance estimate based on the proportion in the control group only, we have 80% power to detect a difference in proportions between those randomized to Clinician-facing Jumpstart and usual care of at least 0.06. We assumed a proportion in the control group of 0.54 based on preliminary data. If the total number of patients with ADRD in Trial 1 is 400 (200 per group), we would have 80% power with $\alpha=0.05$ to detect a difference in proportions of 0.14 among those with ADRD.

Trial 2: With a total sample size of 600 (200 per Clinician-facing Jumpstart, 200 per Bi-directional Jumpstart, and 200 per usual care), we have 80% power to detect a difference in proportions of 16% for each of the 3 pairwise comparisons assuming an overall $\alpha=0.05$ and a Bonferroni adjustment for the 3 comparisons ($\alpha=0.017$ for each comparison) and variance based on a proportion of 0.54.

b) Sample size for qualitative analyses

For Aim 3 qualitative analyses, it is important to achieve theoretical saturation (no new themes emerging).^{64,66} Based on our prior studies, we anticipate achieving saturation by 80 interviews for understanding patients/families and clinician perspectives.^{16,46,54-59} We will monitor for saturation and will recruit additional participants if needed.

8) Data management and quality control to achieve scientific rigor

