 - a. Removing data collection for acute severity of illness (e.g., SOFA score) for Trial 2 and replacing with a NEWS score.
 - b. Revisions to instruments included in surveys for Trial 2
 - c. Increasing subject numbers for clinician interviews from 20 to 50 across both trials
 - d. Addition of demographic items (required by study sponsor, NIH) to the clinician interview
 4. Materials
 - a. Updated instructional video for clinicians in Trial 1
 - b. Revision of the Jumpstart Guide into an HTML format as a delivery option. This version includes optional feedback buttons at the bottom (options: will definitely use; will use if time allows; maybe, will consider; not appropriate; will not see this patient; already done; opt out; other/free text)
 - c. Updated language and formatting for all versions of the Jumpstart Guide (patient, clinician EHR-based, and clinician survey-based) using a human-centered design approach.¹⁰

10) Potential limitations and alternative approaches

a) Including ADRD and other diseases in same study

Patients with ADRD receive different intensity of care at the end of life compared to other chronic diseases,^{73,74} and there may be differences in the effectiveness of the interventions. Our hypothesis is that these interventions will work for all diseases, but because of the unique issues of increasing ICU use among those with ADRD,^{73,74} we will target adequate sample size for patients with ADRD to be able to test this hypothesis for the primary outcome of each trial. We could have proposed separate trials for ADRD and other illnesses, but this would decrease the generalizability of the interventions.

b) Generalizability

This study occurs in a single healthcare system but includes three diverse hospitals thus enhancing generalizability.

c) Misclassification of goals-of-care discussions

Goals-of-care discussions may be misclassified for two reasons: 1) the sensitivity and specificity of the NLP/ML algorithm is not perfect; and 2) documentation of goals-of-care discussions in the EHR will never perfectly reflect actual discussions. This misclassification could affect outcome assessment and patient identification.

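### Optional improvement, not an error: the Trial 1 linear models could also adjust for age, which is known before randomization, for a possible small gain in precision

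*SAP*

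**What the plan says.** The SAP, under General characteristics of analysis, adjusts every regression model for site and ADRD and adds "There will be no other covariates in the models". The interaction and RE-AIM models under Additional analyses carry other terms, so in practice the sentence governs the main treatment-effect models. Protocol section 6a gives the same list and its reason: "The model will adjust for hospital site and ADRD status, since randomization is stratified on these factors".

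The primary analysis is a linear model for a 0/1 outcome with robust standard errors (SAP, Primary outcome). Protocol section 4f states that "Patients are randomized in a 1:1 ratio in Trial 1". The SAP's coding is two-group, "The predictor of interest in all regression models will be the randomization group: 0=control, 1=intervention", which fits Trial 1 and not the three-arm Trial 2.

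Three kinds of baseline information matter here:

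- **Age.** It is an eligibility criterion (protocol opening summary and section 4c) and is listed as collected (section 4d).
- **Qualifying conditions.** Patients are "identified by ICD-10 codes for one or more of the nine chronic conditions" (section 4c). Patients over 80 qualify without one, and section 9, item 1f adds COVID-19 as a Trial 1 inclusion diagnosis.
- **NEWS.** Section 4d lists it without a time of measurement. The one passage that links it to a named trial is section 9, item 3a: "Removing data collection for acute severity of illness (e.g., SOFA score) for Trial 2 and replacing with a NEWS score".

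**The concern.** Stratification is a good reason to include site and ADRD, but it is not a reason to exclude other prognostic baseline variables. Neither document gives such a reason, and neither plans a further-adjusted randomized comparison, even as a sensitivity analysis.

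With 1:1 allocation and a linear model, adding a baseline covariate leaves the target unchanged (a difference in proportions or in means) and does not lose precision in large samples. If age predicts a documented discussion, the primary interval would narrow without enrolling anyone else. So would the separate ADRD estimates, which have only about 200 patients per arm.

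**Working it through.** **Inputs.** Protocol section 7a gives 1000 per arm, two-sided alpha 0.05, 80% power, a control proportion of 0.54 and "a variance estimate based on the proportion in the control group only". It gives 200 per arm for ADRD. The share of remaining variance explained by the added covariates (R²) is not documented; 1%, 5% and 10% are assumptions.

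**Step 1: the plan's own figures.** The variance is 0.54 × 0.46 = 0.2484.

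- Trial 1: SE = √(0.2484 × 2/1000) = 0.02229. The 80%-power difference is (1.960 + 0.842) × 0.02229 = 0.0624, which rounds to the stated 0.06.
- ADRD: SE = √(0.2484 × 2/200) = 0.0498. The difference is 0.1396, which rounds to the stated 0.14.

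Both figures reproduce. At exactly 0.06, power is 76.8%, so the Trial 1 match depends on rounding to two decimals.

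**Step 2: effect of adjustment in Trial 1.** The SE is multiplied by √(1 − R²), the half-width is 1.96 × SE, and power is Φ(0.0624/SE − 1.96), using the unrounded difference.

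| Assumed R² | Half-width (points) | Power at 0.0624 | Power at 0.06 |
|---|---|---|---|
| 0 | 4.37 | 80.0% | 76.8% |
| 1% | 4.35 | 80.4% | 77.2% |
| 5% | 4.26 | 82.0% | 78.9% |
| 10% | 4.14 | 84.0% | 81.0% |

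The interval narrows by 0.5%, 2.5% or 5.1%. In patients, 2000/(1 − R²) gives 2020, 2105 or 2222, that is, about 20, 105 or 222 extra.

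The table treats site and ADRD as explaining nothing. If they already explain 5%, the half-width goes from 4.26 to 4.24, 4.15 or 4.04, and power at 0.0624 from 82.0% to 82.4%, 83.9% or 85.8%. The proportional narrowing is the same.

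**Step 3: cost if the covariates are useless.** Each extra term inflates the variance by roughly 1/n. Two terms cost about 2/2000 = 0.1% overall and 2/400 = 0.5% in ADRD. Age alone, as one term, costs about half of each.

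**Step 4: ADRD net of the two-term cost.** The detectable difference is 0.1396 × √((1 − R²) × 1.0051). That gives 0.1393, 0.1364 or 0.1328. Break-even R² is about 0.5%.

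**Step 5: simulation check.** Each setting had 3000 runs with simple 1:1 allocation, HC1 standard errors, site explaining about 2%, and two uncorrelated, equally predictive covariates.

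| Assumed R² | n=2000, power at 0.0624: planned vs adjusted | n=400, power at 0.1396: planned vs adjusted |
|---|---|---|
| 0 | 80.6 vs 80.4% | 81.3 vs 80.8% |
| 1% | 80.4 vs 81.0% | 80.4 vs 80.5% |
| 5% | 81.7 vs 83.6% | 81.3 vs 83.2% |
| 10% | 79.8 vs 83.4% | 80.0 vs 84.0% |

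At n=2000 the mean estimates agreed within 0.0002. Type I error was 4.6–5.9% planned and 4.8–6.1% adjusted (Monte Carlo SE 0.4 points). The simulation did not use the trial's stratified blocks. It also ignored the link between age and condition count created by the over-80 rule, so it supports the direction of the effect and not a forecast of its size.

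**The case against.** The strongest reply is that this is a preference. Prespecifying only the stratification factors is defensible, the two documents agree, and no stated figure is wrong. That stands, and it is why the point is optional.

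Second, the benefit is assumed. Nothing in the documents says that age predicts a documented discussion. At R² of 1% the half-width moves by 0.02 points and power by 0.4 points, and in ADRD an R² below about 0.5% makes two-term adjustment slightly worse. That stands too.

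Third, the gain may be out of reach. The SAP's mortality entries say that all index discharges were complete and cite an EHR pull of 2/7/22, so outcome data existed. A late change to the primary model needs proof that arm-level results were unseen. The text available for review contains no such record, but front pages were removed, so its absence shows nothing.

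Four stronger readings are tempting and are not supported:

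- **That the plan is biased or deficient.** It is not. It is a valid analysis matched to the stratified design.
- **That a condition count is equally free.** Screening asks only for one or more conditions, and no count variable is named. The count is an inference from the codes, and it needs a rule for patients eligible by dementia, COVID-19 or age over 80 alone.
- **That NEWS is ready to use.** Its timing is not given.
- **That the argument covers Trial 2 or the Cox and logistic models.** The SAP describes two groups, and the linear-model property does not carry over to those models.

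**Conclusion.** The point holds as an optional, low-cost improvement of lowest severity. Age is known before randomization and already collected, and adding it to the Trial 1 linear models keeps the same target. The gain runs from negligible to about 4 points of power (half-width 4.37 to 4.14 points) across assumed R² of 1% to 10%. None of these R² values comes from the documents, and the upper figures may need more than age alone. What remains of the case is a favourable balance of a very small cost against a possible modest gain. The gain reaches the primary result only if the change can be shown to predate sight of results by arm.

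**What to change.** If a dated record shows that arm-level results were unseen, replace the SAP sentence along these lines, and amend protocol section 6a for Trial 1 to match:

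*Trial 1 treatment-effect models fitted by linear regression with robust standard errors adjust for hospital site, ADRD status and age at randomization. The model with site and ADRD alone is reported as a sensitivity analysis. Cox, logistic and cost models adjust for site and ADRD only.*

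If there is no such record, keep the planned primary model and add the age-adjusted model as a labelled sensitivity analysis. The primary interval then does not narrow.

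Add a count of the eight non-dementia qualifying conditions only if the pre-randomization ICD-10 codes used for screening were retained. Dementia is left out because it overlaps the ADRD term. Code zero for every patient with none of the eight, whether eligible by age over 80, dementia or COVID-19 alone. Leave NEWS out unless its pre-randomization timing in Trial 1 is confirmed.

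The cost is two text edits and one or two model terms. There is a credibility risk if the timing of the change is not documented. The linear and the Cox or logistic analyses of the same outcome would also carry different covariates, which the SAP should state.

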## Primary outcome: Documentation of goals-of-care discussion in the EHR during the 30 days after randomization

- Linear regression model with robust standard errors: outcome = 0 if no discussion documented during this time period; 1 if discussion was documented
- Additional analysis, in case required by reviewers: logistic regression.

## Secondary outcomes:

- Timing of goals-of-care discussion during the 30 days after randomization.  
Cox proportional hazards model:  
Outcome coded as for the primary analysis.  
Time = observation time (elapsed days between randomization and whichever came first: observed discussion, death, 30 days after randomization). Censored if outcome=0.
- Mortality at several time points:  
Outcome = death (0=alive at date of mortality status evaluation, 1=died by date of mortality status evaluation)  
TIME POINT #1: death outcome measured from EHR data for the 30 days after randomization.  
TIME POINT #2: death outcome measured from EHR data at time of index hospitalization discharge. (All patients have been discharged from their index hospitalization.)  
TIME POINT #3: death outcome measured from EHR data pulled for analyses on 2/7/22.  
TIME POINT #4: death outcome measured from death certificates covering the year after randomization.  
(a) Linear regression with robust standard errors (logistic regression as additional analysis in case reviewers request it).  
(b) Cox proportional hazards model of time to death.  
The time variable will represent the elapsed days between randomization and whichever came first: death or the date on which mortality status is assessed. Censored if death = 0.
- EHR documentation of whether patient received any ICU care in the 30 days (and also in the 90 days) after randomization  
Linear regression with robust standard errors (logistic regression as additional analysis in case reviewers request it): outcome = 0 if no documentation of ICU care during period of interest; 1 if ICU care occurred during that period
- EHR documentation of whether patient had any ED visits in the 30 days (and also in the 90 days) after randomization  
Linear regression with robust standard errors (logistic regression as additional analysis in case reviewers request it): outcome = 0 if no documentation of ED visits during period of interest; 1 if ED visits occurred during that period

- EHR documentation of any palliative care consultation in the 30 days (and also in the 90 days) after randomization  
Linear regression with robust standard errors (logistic regression as additional analysis in case reviewers request it): outcome = 0 if no documentation of palliative care consultation during period of interest; 1 if PC consultation documented during that period
- EHR documentation of any hospital readmission within specified windows (7 days and 30 days) after discharge from the index hospitalization (excluding apparent readmissions that actually represented hospital transfers):  
Linear regression with robust standard errors; (logistic regression as additional analysis in case reviewers request it): outcome = 0 if no documentation of readmission during period of interest; 1 if readmission occurred during that period.
- Days out of the ICU and alive during specified periods (30 days and also 90 days) after randomization:  
Coding procedure:
  - Step 1: Compute the number of days alive during the period  
If patient died before the end of the period: number of days between randomization and death; If patient alive at the end of the period, number of days in period (30 or 90).
  - Step 2: Compute the number of days in the ICU during the period.
  - Step 3: Outcome measure = days alive minus days in the ICU.

Days-alive and days in ICU will be computed using only the DATES of randomization, death, and ICU admission and discharge. (Times will be ignored.)  
Primary analysis: Linear regression with robust standard errors (logistic regression as additional analysis in case reviewers request it)
- Days out of the hospital and alive during specified periods (30 days and also 90 days) after randomization:  
Coding procedure:
  - Step 1: Compute the number of days alive during the period  
If patient died before the end of the period: number of days between randomization and death; If patient alive at the end of the period, number of days in period (30 or 90).
  - Step 2: Compute the number of days in hospital during the period.
  - Step 3: Outcome measure = days alive minus days in hospital.

Days-alive and days in hospital will be computed using only the DATES of randomization, death, and ICU admission and discharge. (Times will be ignored.)  
Primary analysis: Linear regression with robust standard errors (logistic regression as additional analysis in case reviewers request it)

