Bi-directional Jumpstart (Trial 2 only): First, information about the patient is abstracted from the EHR in the same way as for the Clinician-facing Jumpstart. Second, patients or their legal surrogate decision-maker complete baseline survey items assessing three domains: a) preferences for discussions about goals of care; b) barriers and facilitators for having such discussions; and c) current goals of care. Third, using the EHR and baseline survey, we use the automated algorithm from our prior trial⁹ adapted to the hospital setting using human-centered design methods¹⁰ to create a survey-informed Jumpstart Guide to prompt and guide goals-of-care discussions between the patient and hospital team or, if the patient isn't able, the family member and the hospital team (see supplement for sample Jumpstart Guide). Finally, in the fourth step, we deliver the Jumpstart Guides to the primary team via secure email similar to Trial 1, as well as in-person delivery to members of the team. We also provide a survey-informed Jumpstart Guide to the patient or family, adapted with phrasing and terminology specifically for the patient and family. All Jumpstart Guides are delivered on

the day of randomization with the goal of prompting a goals-of-care discussion early during hospitalization, as supported by the National Quality Forum.¹¹ The bi-directional Jumpstart includes both EHR- and patient-tailored suggestions for conducting goals-of-care discussions based on survey responses. The suggestions are guided by the educational experience of VitalTalk, a nationally-acclaimed program for teaching serious illness communication, and adapted to the inpatient setting,^{12,13} as well as by a human-centered design exercise with hospital clinicians.¹⁰

5) Outcomes

a) Outcomes from the EHR and Death Certificates (Trials 1 and 2):

The primary outcome for both trials is EHR documentation of goals-of-care discussions within 30 days after randomization. Our rationale for this as the primary outcome is that this is the primary target for all interventions and important to diverse stakeholders including patients and their families.^{1,14-17} We will use NLP/ML methods to identify goals-of-care discussions.¹⁸ We will manually review the EHR for goals-of-care discussions using our standard EHR abstraction methods¹⁹⁻²¹ for a randomly selected subset of patients in each trial to evaluate potential misclassification with NLP/ML methods.

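### Cox time is counted in elapsed days with no rule for the day of randomization, so same-day discussions may drop out of the secondary timing analysis

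*SAP*

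**What the plan says.** SAP, Secondary outcomes, timing of discussion: a Cox model with the event coded as in the primary analysis and "Time = observation time (elapsed days between randomization and whichever came first: observed discussion, death, 30 days after randomization". The mortality Cox models use the same unit: "The time variable will represent the elapsed days between randomization and whichever came first: death or the date on which mortality status is assessed". Neither entry has an offset, a minimum time or a same-day convention.

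SAP, General characteristics of analysis, names Stata and its exactp option as the "method for correcting for ties unless there are problems with that method, in which case we will use the Efron method".

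SAP, Primary outcome: a binary indicator, "outcome = 0 if no discussion documented during this time period; 1 if discussion was documented". It makes no use of the time variable.

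SAP, Secondary outcomes, ICU-free days: "Days-alive and days in ICU will be computed using only the DATES of randomization, death, and ICU admission and discharge. (Times will be ignored". The hospital-free-day entry is similar. The SAP does not say this for the Cox time variable.

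Protocol section 4g says that all guides are delivered on "the day of randomization with the goal of prompting a goals-of-care discussion early during hospitalization". Protocol section 6 applies intention to treat to every analysis.

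**The concern.** Subtracting a date from the same date gives 0. A discussion documented on the randomization date is therefore an event with time 0 if whole days are used. Stata's survival set-up by default treats a record ending at time 0 as contributing no time at risk and leaves it out. This is general software knowledge, not a statement in the documents. Such a patient would be a success in the primary analysis and absent from the timing analysis.

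The timing model asks whether the guide brings discussions forward. Delivery is on day 0, so the excluded events could be the most direct evidence of an early effect. Exclusion would be decided by a post-randomization outcome that the intervention targets, which conflicts with the intention-to-treat rule. The comparison would then be between patients who had not yet had a discussion by the end of day 0, and randomization does not protect that comparison.

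**Working it through.** **Inputs.** Protocol section 7a gives 1000 per group, two-sided α 0.05, 54% in control and a difference of 0.06. The documents state no figure for the Cox analyses. As a check on the inputs, the detectable difference is (1.960 + 0.842) × √(2 × 0.54 × 0.46 / 1000) = 0.0624, which agrees with the stated 0.06 after rounding. The day-0 share is not in the documents. I assume 5% in control and vary it from 2% to 15%.

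**Hand calculation at 5%.** If day-0 records are removed, the proportion without a discussion at day 30 among those left is S = (1 − p30)/(1 − p0). The ratio of ln S between arms approximates the hazard ratio (HR) that remains.

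- Control: 0.46/0.95 = 0.4842, ln = −0.7252.
- Whole effect on day 0 (11%, then 49% later): 0.40/0.89 = 0.4494, ln = −0.7998. Ratio 1.10.
- Half on day 0 (8%, then 52% later): 0.40/0.92 = 0.4348, ln = −0.8329. Ratio 1.15.
- Timing shift only (11% on day 0, still 54% by day 30): 0.46/0.89 = 0.5169, ln = −0.6600. Ratio 0.91.
- Proportional effect, HR = ln 0.40/ln 0.46 = 1.18: day-0 share 1 − 0.95^1.18 = 5.9%. Ratio still 1.18.

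Records lost: 50 + 110 = 160 in the first and third scenarios, 50 + 80 = 130 in the second, and about 50 + 59 = 109 in the last.

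**Simulation.** Cox model with Efron ties, arm as the only covariate, no deaths, later discussions front-loaded, 600 runs per scenario, 5% control share:

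| Scenario | HR, day 0 kept | Significant | HR, day 0 dropped | Significant |
|---|---|---|---|---|
| All on day 0 | 1.21 | 89% | 1.10 | 28% |
| Half on day 0 | 1.19 | 81% | 1.14 | 56% |
| Timing shift only | 1.05 | 11% | 0.92 | 25% |
| Proportional | 1.18 | 81% | 1.18 | 77% |

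Repeat simulations of these scenarios gave 1.08 and 1.09 for the first scenario with day 0 dropped (power 23% and 25%), and 1.04 v 0.91 for the timing shift.

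**Range over control shares of 2% to 15%.**

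- All on day 0: HR 1.20–1.21 falls to about 1.10; power falls from 86–90% to 28–29%.
- Half on day 0: HR 1.18–1.19 falls to 1.13–1.16.
- Timing shift only: HR 1.04–1.05 becomes 0.88–0.92.
- Proportional: HR unchanged; power falls from 77–82% to 64–79%.

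**Where the loss comes from.** The partial likelihood uses only the order of event times. In simulated data with day-0 events, a routine that keeps zero times gave the same HR and standard error (1.433, 0.060) as one fitted to time + 1, with all 2000 patients used. The loss therefore comes from excluding zero-time records.

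**The case against.** The SAP's rule removes nobody by itself. A reader might infer that any Cox analysis of these times loses the day-0 events. That is not so: software that keeps zero times as the earliest tied time uses them in full. The point depends on Stata's default, and the SAP names Stata only in its ties rule. This stands, and it limits the point to the named software.

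Whole days are also inferred. The SAP says clock times are ignored for the free-day outcomes and does not say so for the Cox models. With fractional days from time-stamps, the problem largely disappears. Against that, a planned exact method for ties, with a fallback, suggests that many ties are expected, as whole-day times would produce. The ties bullet refers to page 4, but the SAP text available for review contains no same-day rule.

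A reader might infer that the guide arm must lose more patients. The documents give no day-0 share in either arm. The day-of-delivery sentence covers all guides but sits in the paragraph on the Trial 2 guide; the paragraph on the clinician-facing guide gives no day. The scenario with the whole effect on day 0 is an extreme, and a proportional effect leaves the HR unchanged.

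A reader might also object to exactp because its coefficient is an odds ratio, while the Efron fallback gives a hazard ratio. The choice is prespecified and matters little here. A 54% proportion over 30 days implies a mean daily hazard of 1 − 0.46^(1/30) = 0.026, at which a true HR of 1.20 would read as 1.203. No change of ties method is warranted.

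**Conclusion.** The point holds as a gap with a possible bias. The SAP has no rule for an event on the randomization date, and following it with whole days in Stata's default set-up would exclude patients whom the primary analysis counts as events. Depending on how much of the effect falls on day 0, the timing HR could be unchanged, attenuated (about 1.20 to 1.08–1.10 at most in these scenarios) or reversed (1.04 to about 0.91 for a pure timing shift).

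This rests on three assumptions: whole-day times, the software default left in place, and the assumed day-0 shares. Only the secondary Cox models are touched. A reader might extend the concern to the primary result, but that is a 30-day indicator and does not use the time variable. The mortality models share the coding, but the effect there needs deaths on the randomization date and is probably small. The change is worth making because it costs almost nothing and the timing estimate could otherwise point the wrong way.

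**What to change.** In the SAP, for all Cox models:

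1. Define time as elapsed days + 1 (randomization day = day 1) or + 0.5, or use time-stamps and count only discussions after randomization. With dates alone, a same-day discussion cannot be placed before or after randomization. If time-stamps are used for that purpose, apply the same rule to the primary indicator.
2. State that no randomized patient is excluded because of zero time.
3. Check that the number of patients and of events in the timing model equal those in the primary analysis, and report day-0 discussions and deaths by arm.

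The ties method can stay as planned. Adding an offset costs a sentence or two in the SAP and one line of code, with no new data; the time-stamp option needs the times of EHR notes.
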